#### 9.2.2. Health-Related Quality of Life

HRQoL will be assessed at baseline, at the beginning of cycles 3 day 1, cycle 5 day 1, end of cycle 6 and 3 months after completion of study.

#### Bone

Collagen type IC teleopeptide, procollagen Type I Intact N-terminal peptide, bone specific alkaline phosphatase. Should be done while fasting. Please see study calendar.

#### The Expanded-Prostate Index Composite – 26 (EPIC 26)

EPIC-26 evaluates patient's urinary incontinence (4 items), urinary irritation/obstruction (4 items), bowel (6 items), and vitality/hormonal function (5 items). All domains are reported on a scale of 0 – 100. EPIC is a robust prostate cancer HRQoL instrument that measures a broad spectrum of symptoms and has 50 items; however, to decrease patient burden only the domains most pertinent to this study will be used as represented in the EPIC-26. EPIC-26 has been validated in men with localized prostate cancer who underwent surgery, external beam radiation, or brachytherapy with or without the use of hormonal adjuvants. Further information on EPIC can be found at the University of Michigan website: <http://www.med.umich.edu/urology/research/epic.html>.

#### Patient-Reported Outcome Measurement Information System (PROMIS)-Fatigue Short Form

PROMIS was developed as part of the NIH Roadmap Initiative, focused on developing a publicly available resource of standardized, accurate, and efficient PRO measures of symptoms, distress, and functioning. Two content domains of fatigue, experience and impact, were identified by a panel of experts. An item pool of 58 fatigue experience and 54 fatigue impact items were developed. The psychometric properties of these items were evaluated in a sample of 450 individuals from the general US population using classical test theory indices, monotonicity, and scalability. The expert panel selected the 10 best items in each domain. These 20 items were presented to a panel of clinical experts. Only one item was dropped because of redundancy. A fatigue short-form measure of 7 items was created using items selected for consistency in the response scale, broad coverage across the fatigue continuum (i.e., high to low), and good precision of measurement (discrimination function).

## Pittsburgh Sleep Quality Index (PSQI)

Sleep quality will be measured by the PSQI, a self-rated questionnaire which measures sleep quality and disturbances. The Pittsburgh Sleep Quality Index was developed to discriminate between good and poor sleepers. The PSQI has good internal consistency (Cronbach's alpha=0.83), stability (test-retest reliability=.85, P<.001) and discriminant validity. It has been used in patients with cancer and demonstrated sleep problems as expected

## 9.3 Serum Hormone Levels

Serum hormone levels include DHEA sulfate, estrone, free testosterone, total testosterone, estradiol (estrogen), androstenedione. These should be done while fasting.

See Study Calendar (Section 9) for the measurement time points.

## 9.4 Anthropomorphic Measures

Anthropomorphic measurements include Triceps skin fold, mid-upper arm circumference (biceps), shoulder blade and waist. (Section 8). Skin measurements will be done using Slim Guide Skinfold Caliper. Skin Measure will be taken at four different areas as below. A standard caliper will be supplied to all sites.

Measurement of body fat percentage is done using skinfold caliper by adding the measurements at four different locations (Triceps, Biceps, Shoulder blade and Waist).

### Back of Upper Arm (right):

[figure not shown]
The back of upper arm (Triceps) is located halfway between the shoulder and elbow joints. The skinfold is taken

in a vertical direction on the center of the back of the arm.

### Front of Upper Arm (right)

The Front of upper arm (Biceps) is located halfway between the shoulder and elbow joints. The skinfold is taken in a vertical direction on the center of the front of the arm.

[figure not shown]
**Upper Back (right):**

Located just below the shoulder blade (Subscapular). The skinfold is taken at a 45° angle.

[figure not shown]
**Waist (right):**

Waist (Suprailiac) is located just above the iliac crest, the protrusion of the hip bone, a little towards the front from the side of the waist. The skinfold is taken horizontal.

[figure not shown]

**Skinfold Testing Technique**

Use your thumb and index finger of your left hand to pinch an area of skin wide enough to get a good fold.

[figure not shown]
Pull out the fold of skin and underlying layer of fat with your left hand away from the body. You do not have to worry about getting any muscle as the muscle is firm and will not come into a fold with the skin and fat.

CONFIDENTIAL

This document is confidential. Do not disclose or use except as authorized.

While holding the skinfold with the left hand, place the jaws of the calipers about 1/4" from the fingers of the left hand. Release the trigger of the caliper so the entire force of the jaws are on the skinfold. Without releasing the skinfold with the left hand, let the force of the caliper creep a bit for a few seconds to settle to the correct reading. Write down the measurement and proceed to the next location.

[figure not shown]

Measurement of lean muscle mass is done by multiplying the weight (in lbs.) by the body fat percentage. See Appendix G.

The breast enlargement assessment will be done with calipers. The maximum diameter of the larger breast (if there is asymmetry) at Baseline (Day One Cycle 1), Cycle 4/day 1, End of Cycle 6 and assess it according to these parameters: grade 1 ( $\leq 2$ cm), grade 2 ( $> 2 - \leq 4$ cm), grade 3 ( $> 4 - 6$ cm), and grade 4 ( $> 6$ cm).

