### 1.3 Secondary Objectives

1. Assessment of the effect of treatment on health-related quality of life including fatigue, sleep quality, as well as urinary, bowel, sexual and hormonal functioning.
2. Assessment of the effect of treatment on serum sex hormones including androgens and estrogens.
3. Assessment of the effect of treatment on body fat distribution and muscle mass.
4. Assessment of safety and tolerability according to adverse event reporting during the trial.
5. Assessment of the effect of treatment on bone metabolism.

CONFIDENTIAL

This document is confidential. Do not disclose or use except as authorized.

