### **2.3 Rationale**

Presently most patients with intermediate risk prostate cancer receive neoadjuvant, concurrent and adjuvant hormonal therapy with external beam irradiation. Multiple studies have shown that the addition of HT improves survival to external beam radiation (5,6) However androgen deprivation induced by LH-RH agonists consistently results in hot flashes, loss of libido, loss of sexual functioning, weight gain, changes in metabolism, loss of muscle mass and fatigue (7, 8).

In contrast, treatment with the anti-androgens bicalutamide or flutamide has minimal side effects, likely related to the fact that these agents do not suppress serum testosterone. Enzalutamide has the potential to have similar anti-tumor effects as LH-RH agonist without the toxicity associated with castrate testosterone levels. If it were shown that enzalutamide (enzalutamide) could be used as an effective adjuvant treatment for prostate cancer without androgen deprivation it would have dramatic and significant impact, including expanding its use to those patients who may have more intermediate risk and/or are unable to tolerate the toxicities associated with androgen deprivation

We have chosen as the primary endpoint the assessment of the proportion of patients whose PSA level is  $\leq 0.2$  ng/ml at the conclusion of therapy. This endpoint was chosen because patients that

CONFIDENTIAL

This document is confidential. Do not disclose or use except as authorized.

Version 13.0 Protocol Version Date: 1/09/2015

achieve this value after treatment with LHRH analogs in combination with EBRT have an excellent prognosis compared to patients that demonstrate higher PSA levels (1, 9). Furthermore, demonstration of PSA levels of  $\leq 0.2\text{ng/ml}$  in a significant number of patients treated on this study would be strong motivation to perform a phase III randomized trial comparing enzalutamide to LHRH analog therapy in the same setting.

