13.2.4. Anthropomorphic Measurements: Descriptive statistics at each time point and change over 6 cycles will be provided for all anthropomorphic measures.

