### Chart (Men)

% Fat for Sum of Measurements at All 4 Locations

Sum in mm	Age 16-29	Age 30-49	Age 50+
20	8.1	12.1	12.5
22	9.2	13.2	13.9
24	10.2	14.2	15.1
26	11.2	15.2	16.3
28	12.1	16.1	17.4
30	12.9	16.9	18.5
35	14.7	18.7	20.8
40	16.3	20.3	22.8
45	17.7	21.8	24.7
50	19.0	23.0	26.3
55	20.2	24.2	27.8
60	21.2	25.3	29.1
65	22.2	26.3	30.4
70	23.2	27.2	31.5
75	24.0	28.0	32.6
80	24.8	28.8	33.7
85	25.6	29.6	34.6
90	26.3	30.3	35.5
95	27.0	31.0	36.5
100	27.6	31.7	37.3
110	28.8	32.9	38.8
120	29.9	34.0	40.2
130	31.0	35.0	41.5
140	31.9	36.0	42.8
150	32.8	36.8	43.9
160	33.6	37.7	45.0
170	34.4	38.5	46.0
180	35.2	39.2	47.0
190	35.9	39.9	47.9
200	36.5	40.6	48.8

CONFIDENTIAL

This document is confidential. Do not disclose or use except as authorized

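### The formula given for lean muscle mass computes fat mass, so the muscle-mass result is wrong in size and, at stable weight, reversed in sign

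*Combined protocol and SAP*

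**What the plan says.** Secondary objective 3 (Section 1.3) is "Assessment of the effect of treatment on body fat distribution and muscle mass". Section 9.4 supplies the derivation. Caliper readings at triceps, biceps, shoulder blade and waist are added, and Appendix G turns the sum into a percentage; its chart for men is headed as percentage "Fat for Sum of Measurements at All 4 Locations". The muscle measure then follows in the skinfold technique text: "Measurement of lean muscle mass is done by multiplying the weight (in lbs.) by the body fat percentage", with a pointer to Appendix G.

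On the biceps input, the opening sentence of Section 9.4 reads "Anthropomorphic measurements include Triceps skin fold, mid-upper arm circumference (biceps), shoulder blade and waist", and footnote 3 of the study calendar (Section 8) also equates biceps with mid-upper-arm circumference. The technique text for the front of the upper arm describes a caliper fold: "The skinfold is taken in a vertical direction on the center of the front of the arm".

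Section 13.2.4 gives the analysis: "Descriptive statistics at each time point and change over 6 cycles will be provided for all anthropomorphic measures".

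**The concern.** The derivation names one quantity and calculates its complement. Appendix G offers no rescue, since it stops at percentage fat and contains no subtraction step.

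The direction of the error is what makes it serious. Section 2.3 lists "weight gain, changes in metabolism, loss of muscle mass and fatigue" among the consistent effects of LH-RH agonists, and Section 1.1 expects enzalutamide to do much better on the secondary outcomes, with convincing data leading to a Phase III comparison. A man who gains fat and loses lean tissue would be recorded as gaining lean muscle mass, so harm would read as benefit. The trial has one arm, so no concurrent comparator would expose the mistake.

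The biceps wording is a smaller, related problem. A circumference entered into a sum built for four skinfolds would invalidate the percentage fat on which both body-composition results depend.

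**Working it through.** The plan states no numerical result, power or effect size for lean mass, so there is no figure to reproduce. The check is an identity plus worked values.

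**Inputs**
- Percentage fat (B): Appendix G, age 50+ column. 20 mm = 12.5%, 50 mm = 26.3%, 55 mm = 27.8%, 60 mm = 29.1%, 200 mm = 48.8%.
- Weight (W): not given in the documents. Assumed 200 lb for the main example, with a range of 160 to 220 lb.

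**Formulas**, taking the percentage as a fraction
- Written rule: W × B/100
- Fat mass: W × B/100, identical to the written rule
- Lean (fat-free) mass: W × (1 − B/100)

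**Size of the error at 50 mm (26.3%)**

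| Weight (lb) | Written rule (lb) | Lean mass (lb) |
|---|---|---|
| 160 | 42.1 | 117.9 |
| 190 | 50.0 | 140.0 |
| 200 | 52.6 | 147.4 |
| 220 | 57.9 | 162.1 |

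The ratio does not depend on weight: 0.263/0.737 = 0.36. Across the age 50+ column it runs from 0.125/0.875 = 0.14 to 0.488/0.512 = 0.95. Every value in that column is below 50%, so the rule always understates lean mass there.

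**Sign of the change at constant weight.** Take 200 lb, with the sum rising from 50 to 60 mm.
- Written rule: 200 × 0.291 − 200 × 0.263 = 58.2 − 52.6 = +5.6 lb
- Lean mass: 200 × 0.709 − 200 × 0.737 = 141.8 − 147.4 = −5.6 lb

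The shift is W × 0.028, so it is 4.5 lb at 160 lb and 6.2 lb at 220 lb, always with opposite signs.

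**Sign of the change when weight moves.** Weight is fat plus lean, so the reported change equals the weight change minus the true lean change.

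| Weight (lb) | Skinfold sum (mm) | Written rule (lb) | Lean mass (lb) | Sign |
|---|---|---|---|---|
| 190 to 194 | 50 to 60 | +6.5 | −2.5 | reversed |
| 190 to 194 | 50 to 50 | +1.1 | +3.0 | same, wrong size |
| 190 to 200 | 50 to 55 | +5.6 | +4.4 | same, wrong size |

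Reversal is therefore exact at stable weight. It also occurs whenever fat and lean mass move in opposite directions. When they move together the sign is right and the size is wrong.

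**Biceps input.** The documents give no arm circumference. An assumed 250 to 350 mm would, on its own, exceed the 200 mm maximum of the Appendix G sum.

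**The case against.** The strongest reply concerns weight rather than fact. Muscle mass is half of one of five secondary objectives, and Section 13.2.4 plans descriptive statistics only, with no test or decision rule. The schema and Section 1.1 name body fat measurements, not muscle, as the endpoint. Percentage fat is derived correctly, and the primary endpoint, sample size and error rates in Section 13.1 are untouched. The sentence may be a drafting slip, and a 200 lb man with 52.6 lb of lean mass would look implausible to an analyst. Weight and the skinfold sites are scheduled at baseline and the end of cycle 6, so the value can be recomputed. All of this stands. It limits the damage and makes the repair cheap, but it does not make the written rule correct.

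It is also fair that sign reversal is not universal: with enough weight gain both quantities rise. That is why the claim of an exactly reversed sign is confined to stable weight. The pattern of most interest, fat gained and lean tissue lost, is reversed whatever the weight does.

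On the biceps, Section 9.4 goes on to say that percentage fat comes from caliper readings at four sites, and the technique text plainly describes a fold. A circumference would also overshoot the chart and so be noticed. The point is therefore lesser, but the conflicting wording in the opening of Section 9.4 and in calendar footnote 3 is real. A site working from the calendar could record the wrong thing, and percentage fat could not then be recovered from that chart.

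**Conclusion.** The concern holds. If the written rule is followed, the plan reports fat mass under the name of lean muscle mass. Over the age 50+ chart the reported value is 0.14 to 0.95 times the true lean mass, and 0.36 times at 26.3% fat. At constant weight the change is equal in size and opposite in sign: plus versus minus 5.6 lb in the 200 lb example. The ratios rest only on Appendix G and the identity that weight is fat plus lean; the pound figures also rest on the assumed weights.

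The effect is confined to the muscle-mass part of secondary objective 3, but it must be corrected before that result is reported. Even the corrected quantity is fat-free mass, which is not the same as muscle mass.

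**What to change.** - In Section 9.4, replace the sentence with two definitions: fat mass = weight × (% fat/100), and fat-free (lean) mass = weight × (1 − % fat/100). Label the second as fat-free mass in the analysis, and note in objective 3 that it stands in for muscle mass.
- In the opening sentence of Section 9.4 and in calendar footnote 3, name the biceps skinfold as the fourth input to the Appendix G sum. If arm circumference is wanted, record it as a separate variable.
- Recompute any values already derived, and check which biceps measure each site recorded.

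The cost is a few wording edits and one recalculation. No new data are needed where a biceps skinfold was taken. Where only a circumference was recorded, percentage fat and fat-free mass cannot be derived from the Appendix G chart and should be reported as missing.

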#### **Technique for measuring male breast tissue:**

Proper technique is needed to examine the male breast. The thumb and index finger are used to grasp and gently pinch the periareolar area of the breast and to palpate glandular breast tissue, which is rubbery in consistency and firmer than the surrounding adipose tissue. With this technique, gynecomastia can usually be distinguished from excessive breast adipose tissue, called pseudo gynecomastia, which is often associated with generalized obesity. Gynecomastia is usually bilateral and relatively symmetric, but occasionally it is asymmetric and more prominent on one side. If present, asymmetric gynecomastia may suggest breast carcinoma, which is usually rock-hard and irregular and may be associated with skin dimpling (peau d'orange), nipple retraction or discharge, and axillary lymphadenopathy. The diameter of palpable breast tissue is used as an objective measure of gynecomastia. Gynecomastia of recent onset is usually tender on palpation, and men usually complain of nipple irritation associated with rubbing against clothing. The proper method of examining the male breast is to use the thumb and index finger to grasp the periareolar area of the breast and to gently pinch the thumb and index finger together on either side of the breast toward the nipple. Glandular breast tissue feels like a rubbery disc of tissue that extends concentrically from under the nipple and subareolar area and is firmer than the surrounding adipose tissue. The size of gynecomastia is estimated by measurement of the diameter of palpable breast tissue.

**Figure 2. Differentiation of Gynecomastia from Pseudogynecomastia and Other Disorders by Physical Examination.**

The patient lies flat on his back with his hands clasped beneath his head. Using the separated thumb and forefinger, the examiner slowly brings the fingers together from either side of the breast. In patients with true gynecomastia, a rubbery or firm mound of tissue that is concentric with the nipple-areolar complex is felt, whereas in patients with pseudogynecomastia, no such disk of tissue is found.

## 9.5 Correlative Endpoint

Prostate biopsy samples from patients obtained during fiducial placement will be formalin fixed and paraffin embedded analogous to routine prostate biopsies. Freshly cut sections will be stained for AR using commercially available antibodies. Patient samples that have tumor will be analyzed for AR overall expression. High powered tumor sections demonstrate that at least 50% of the tumor cells express AR. These will be graded for nuclear expression as none, rare, less than expression in the cytoplasm or greater or equal to cytoplasmic expression.

Please page the study coordinator, [name] at [contact] and [name] at [contact] or page through the BIDMC operator at [name].

## 10. ADVERSE EVENT REPORTING REQUIREMENTS

### 10.1 Definitions 10.1.1 Adverse

Event (AE)

An adverse event (AE) is any undesirable sign, symptom or medical condition or experience that develops or worsens in severity after starting the first dose of study treatment or any procedure specified in the protocol, even if the event is not considered to be related to the study.

Abnormal laboratory values or diagnostic test results constitute adverse events only if they induce clinical signs or symptoms or require treatment or further diagnostic tests. **10.1.2 Serious adverse event (SAE)**

A serious adverse event (SAE) is any adverse event, occurring at any dose and regardless of causality that:

- Results in death

CONFIDENTIAL

This document is confidential. Do not disclose or use except as authorized.

- Is life-threatening. Life-threatening means that the person was at immediate risk of death from the reaction as it occurred, i.e., it does not include a reaction which hypothetically might have caused death had it occurred in a more severe form.
- Requires or prolongs inpatient hospitalization (i.e., the event required at least a 24-hour hospitalization or prolonged a hospitalization beyond the expected length of stay). Hospitalization admissions and/or surgical operations scheduled to occur during the study period, but planned prior to study entry are not considered SAEs if the illness or disease existed before the person was enrolled in the trial, provided that it did not deteriorate in an unexpected manner during the trial (e.g., surgery performed earlier than planned).
- Results in persistent or significant disability/incapacity. Disability is defined as a substantial disruption of a person's ability to conduct normal life functions.
- Is a congenital anomaly or birth defect; or
- Is an important medical event when, based upon appropriate medical judgment, it may jeopardize the participant and require medical or surgical intervention to prevent one of the outcomes listed above. Examples of such medical events include allergic bronchospasm requiring intensive treatment in an emergency room or at home; blood dyscrasias or convulsions that do not result in inpatient hospitalization, or the development of drug dependency or drug abuse.

Events **not** considered to be serious adverse events are hospitalizations for:

- routine treatment or monitoring of the studied indication, not associated with any deterioration in condition, or for elective procedures
- elective or pre-planned treatment for a pre-existing condition that did not worsen
- emergency outpatient treatment for an event not fulfilling the serious criteria outlined above and not resulting in inpatient admission
- respite care

### 10.1.3 Expectedness

Adverse events can be 'Expected' or 'Unexpected.'

#### 10.1.3.1 Expected adverse event

Expected adverse events are those that have been previously identified as resulting from administration of the agent. For the purposes of this study, an adverse event is considered expected when it appears in the current adverse event list, the Investigator's Brochure, the package insert or is included in the informed consent document as a potential risk.

Refer to Section 6.1 for a partial listing of expected adverse events associated with the study agent(s). 10.1.3.2 Unexpected adverse event

For the purposes of this study, an adverse event is considered unexpected when it varies in nature, intensity or frequency from information provided in the current adverse event list,

Version 13.0 Protocol Version Date: 1/09/2015  
the Investigator's Brochure, the package insert or when it is not included in the informed consent document as a potential risk.

#### **10.1.4 Attribution**

Attribution is the relationship between an adverse event or serious adverse event and the study treatment. Attribution will be assigned as follows:

- Definite – The AE is clearly related to the study treatment.
- Probable – The AE is likely related to the study treatment.
- Possible – The AE may be related to the study treatment.
- Unlikely - The AE is doubtfully related to the study treatment.
- Unrelated - The AE is clearly NOT related to the study treatment.

